6.2.4. FVIII Activity Level from Week 12 through 15 Months Postinfusion

The FVIII activity level will be calculated for each participant as a geometric mean of all eligible FVIII activity measures from Week 12 through 15 months post PF-07055480 infusion using the ‘Efficacy’ population. Imputation rules for FVIII activity as described in [Section 3.2.4](#) will be applied. The number of participants (n), mean, standard deviation, median, Q1, Q3, min, max, and 95% CI of mean will be reported in the summary tables. No hypothesis testing will be performed for the geometric mean of FVIII activity level.

6.2.5. FVIII Activity Level by Visit

FVIII activity data in the ‘Dosed’ population will be summarized by visit up to data cutoff with descriptive statistics and 95% CI of mean. Imputation rules as described in [Section 3.2.5](#) will be applied. Order statistics (consisting of minimum, percentiles at 10%, 25%, 50%, 75%, and 90%, and maximum) will be provided for FVIII activity data at Weeks 26, 52 (Month 12), 65 (Month 15), 104 (Year 2), and 156 (Year 3).

FVIII activity will be imputed with 0.9% through data cutoff after the participants have resumed prophylaxis regimen and after they discontinued from the study due to lack of efficacy. In addition, the number and percentage of participants with FVIII activity $\geq 40\%$ will be reported by visit. No hypothesis testing will be performed.

A box-and-whisker plot with study week in the X-axis and FVIII activity level (% of normal) in the Y-axis will be provided for each assay method from central laboratory starting from Week 3 since prophylaxis treatment is allowed during the first 2 weeks postinfusion. The onset of FVIII activity steady state will be assessed by a visual inspection on the box-and-whisker plot for the FVIII activity data based on the central chromogenic assay.

The following supplementary plots (to include appropriate FVIII activity data that were collected beyond 72 hours after administering FVIII infusion with standard half-life or 120 hours with extended half-life products) will be generated for the ‘Dosed’ population.

- The FVIII activity (from central chromogenic assay) along with FVIII activity from one-stage assay (central, local) will be visualized in a scatter plot with chromogenic assay results on the x-axis and one-stage assay results (central and local separately) on the y-axis. Missing data (including discontinuation from the study) won’t be imputed and data post prophylaxis resumption will be excluded. The Pearson’s correlation will be calculated for each pair of the chromogenic vs one-stage assays.

- An additional scatter plot of FVIII activity from central one-stage assay versus FVIII activity from local one-stage assay with central results on the x-axis and local results on the y-axis. Missing data (including discontinuation from the study) won't be imputed and data post prophylaxis resumption will be excluded. The Pearson's correlation will be calculated and provided.
- A spaghetti plot including all participant-level FVIII activity levels postinfusion for each assay method separately from central laboratory over time to data cutoff, including FVIII activity imputation rules described in [Section 3.2.5](#).
- Individual plots presenting all FVIII activity data (initial and retested results) will be provided for the participants who had samples collected while using DOAC before implementing the further validated assays.

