8.1.2. Factor VIII activity

8.1.2.1. General Information About Planned Assays

All samples collected from participants for plasma factor VIII activity levels will be analyzed by central and local laboratories.

- In the central laboratory, FVIII activity will be assessed both by chromogenic and one-stage clotting assay.
- In local laboratories, FVIII activity will be assessed by chromogenic or one-stage clotting assay based on standard practice.

Primary and secondary objectives are based on the chromogenic assay and results will be used to determine steady-state vector-derived circulating FVIII activity levels. As an exploratory objective, both assays performed in central laboratories will be compared.

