8.1.2.3. Guidance Related to Elevated FVIII Activities and Stopping Rule

Participants with FVIII activity levels >ULN should be managed according to the recommendations provided in the “Management Guide for Elevated Factor VIII Activity Levels.”

The guide includes recommendations based on thresholds of FVIII activity levels with 2 main situations described:

- (1) participants with elevated FVIII activity levels from 150% to 230% via central or local chromogenic assay or from 230% to 400% via local one-stage assay, and;
- (2) participants with elevated FVIII Levels $\geq 230\%$ via local or central chromogenic assay or $\geq 400\%$ via local one-stage assay.

According to these levels and after the review of participant's current condition, underlying disease, medical history and risk factors including but not limited to smoking, BMI, prior history of thrombotic event, malignancy, family history, lifestyle, as well as thrombophilia and cardiovascular risk factors, initiation of prophylactic/preventative dose anticoagulation in participants should be considered. Additional laboratory parameters can be recommended (also refer to [Section 8.2.7](#)).

FVIII activity may be impacted by corticosteroid treatment. This should be taken into consideration for corticosteroid dosing and weaning.

In the case of an initial thrombotic event suspected to be related to $>\text{ULN}$ FVIII activity levels for a participant, the study will be paused and no additional participant will be treated until the circumstances for such an event are assessed and regulatory agencies are notified, if required. In the event of recurrence of a thrombotic event in a participant, the DMC will be convened urgently to assess the event. DMC recommendations will be taken into account in the decision to pause the study.

Should the study be paused, the trial re-start will only be possible after Regulatory Authority approval via substantial amendment, where applicable, based on local/regional regulatory requirements.

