Exploratory	Comparison of FVIII activity assays and other exploratory analyses will be described in the SAP finalized before database lock.

Category of Endpoint	Primary Analysis Statistical Analysis Methods
Category of Endpoint	Ultrasound Substudy
Exploratory	Joint images will be reviewed following the extended ultrasound scale with a final score combining soft tissue and osteochondral subscores, and compared to screening (at Week 24 and Week 52 (or EOSV)).
Category of Endpoint	Vector Shedding Substudy
Exploratory	A subset of participants (N=12) will have more extensive vector shedding analysis performed to further characterize the kinetics of vector shedding.
Category of Endpoint	Joint X-Ray Substudy
Exploratory	X-ray assessments will be performed to assess damage within joints as detectable at a radiologic level. X-rays will be acquired at Screening or not later than Week 4/Visit 6, Week 156, and Week 260 or Early Discontinuation Visit.

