3.2.4. FVIII Activity Level from Week 12 through 15 Months Postinfusion

The beginning of steady state will be considered as Week 12 for analysis purposes within this Phase 3 study. Additionally, the data from this Phase 3 study will be utilized to confirm the timing of the onset of steady state.

The Factor VIII activity from Week 12 through 15 months postinfusion will be calculated for each participant as a geometric mean of all appropriate FVIII activity measures (including unscheduled visit observations) from Week 12 through 15 months (up to the upper bound of the Month 15 visit window: Week 67) after PF-07055480 infusion based on central chromogenic assay and one-state clotting assay separately. When multiple appropriate FVIII activity observations are collected on the same day for a participant, the average level of these observations will be used for that given day. FVIII activity will be imputed with 0.9% after the participants have resumed prophylaxis regimen up to data cutoff or Week 67, whichever occurs earlier.

If a participant has missing data for a study visit or has otherwise discontinued due to any reasons other than lack of efficacy but has not resumed prophylaxis prior to completing the designated follow-up period, all available data will be included to calculate geometric mean despite the missed measurements. Specifically, imputation of FVIII activity will be applied per scenarios listed below:

- Resumed prophylaxis but remained in the study: Impute FVIII activity with 0.9% at any protocol-defined visits post resumption of prophylaxis until data cutoff or Week 67, whichever occurs earlier.
- Resumed prophylaxis and then discontinued from the study due to any reasons: Impute FVIII activity with 0.9% at any protocol-defined visits post resumption of prophylaxis until data cutoff or Week 67, whichever occurs earlier.
- Discontinued from study due to lack of efficacy but has not resumed prophylaxis: Impute FVIII activity with 0.9% at any protocol-defined visits post study discontinuation until data cutoff or Week 67, whichever occurs earlier.
- Discontinued from the study due to any reasons other than lack of efficacy but has not resumed prophylaxis: No imputation will be applied. FVIII activity after study discontinuation will be considered missing.

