3.2.5. FVIII Activity Level by Visit

Mapping for unscheduled visit observations and exclusion in FVIII activity data are described in [Section 3.2.1](#). FVIII activity analyzed by the central laboratory will be reported for chromogenic assay and one-state clotting assay separately. FVIII activity will be imputed with 0.9% through data cutoff after the participants have resumed prophylaxis regimen and after they discontinued from the study due to lack of efficacy. FVIII activity won't be imputed after participants discontinue from the study due to reasons other than lack of efficacy if they have not resumed prophylaxis. Specifically, imputation of FVIII activity will be applied per scenarios listed below:

- Resumed prophylaxis but remained in the study: Impute FVIII activity with 0.9% at any protocol-defined visits post resumption of prophylaxis until data cutoff.
- Resumed prophylaxis and then discontinued from the study due to any reasons: Impute FVIII activity with 0.9% at any protocol-defined visits post resumption of prophylaxis until data cutoff.
- Discontinued from study due to lack of efficacy but has not resumed prophylaxis: Impute FVIII activity with 0.9% at any protocol-defined visits post study discontinuation until data cutoff.
- Discontinued from the study due to any reasons other than lack of efficacy but has not resumed prophylaxis: No imputation will be applied. FVIII activity after study discontinuation will be considered missing.

FVIII activity levels by visit will be summarized. In addition, the percentage of participants with FVIII activity level $\geq 40\%$ will be reported by visit up to data cutoff.

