3.3.5. Effects on Coagulation

To evaluate for any effects on coagulation, the following assessments will be performed:

- Coagulation activation tests: aPTT, INR, D-dimer, TGA, TAT.
- Comparison of FVIII activity between one stage assay and chromogenic assay.
- Recovery of FVIII products post gene therapy.

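### Pearson's r is the only paired statistic planned for comparing the FVIII assays, and it cannot register a systematic difference between them

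*SAP*

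**What the plan says.** The endpoint is worded in SAP 3.3.5 as "Comparison of FVIII activity between one stage assay and chromogenic assay", under the exploratory objective on coagulation. Protocol 8.1.2.1 says: "As an exploratory objective, both assays performed in central laboratories will be compared". Neither defines what the comparison is meant to estimate. Protocol 9.4.1 defers the method: "Comparison of FVIII activity assays and other exploratory analyses will be described in the SAP finalized before database lock".

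The method is in SAP 6.2.5, among the supplementary plots. Central chromogenic and one-stage results "will be visualized in a scatter plot with chromogenic assay results on the x-axis and one-stage assay results (central and local separately) on the y-axis", and Pearson's "correlation will be calculated for each pair of the chromogenic vs one-stage assays". A further scatter plot with Pearson's r sets central against local one-stage. The SAP does not plan a ratio, mean difference, regression slope, concordance coefficient or limits of agreement for any pair.

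The SAP also summarises each central assay on its own. Section 3.2.5 states: "FVIII activity analyzed by the central laboratory will be reported for chromogenic assay and one-state clotting assay separately". The participant-level geometric mean in Section 3.2.4 covers Week 12 to Month 15 "after PF-07055480 infusion based on central chromogenic assay and one-state clotting assay separately". Section 6.2.1.2 tabulates participants by FVIII category for each assay, with stacked bar charts, and Section 6.2.5 adds box plots and spaghetti plots by central assay.

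**The concern.** The documents expect a systematic difference. Protocol 8.2.8 warns that the one-stage assay may read higher, and Protocol 9.4 and SAP 3.2.1 choose the central chromogenic assay because it gave the lowest readings in the Phase 1/2 study. Pearson's r measures how closely pairs follow a straight line, whatever its slope or intercept, so it carries no information about that difference. It also depends on how widely FVIII levels vary between participants.

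At stake is the usefulness of a listed exploratory endpoint. The report would give a correlation for each pair but no paired estimate of how far apart the assays read, how precisely that is known, or whether the gap changes with FVIII level. The gap is widest for local one-stage results, which have no planned descriptive summary.

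**Working it through.** The plan states no sample size, precision or hypothesis for this comparison, so there is no figure to reproduce.

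**Inputs from the documents**
- Planned statistic and plots: SAP 6.2.5.
- Expected direction: Protocol 8.2.8 and 9.4, SAP 3.2.1.
- Illustrative ratios: Protocol 8.1.2.3 groups participants with levels "from 150% to 230% via central or local chromogenic assay or from 230% to 400% via local one-stage assay". The paired limits give 230/150 = 1.53 and 400/230 = 1.74. They are used here only as convenient sizes.

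**Assumptions not in the documents**
- One simulated set of 50 pairs.
- Chromogenic values log-normal, with median 30% and log-scale SD 1.0.
- One-stage = k × chromogenic × log-normal error with log-scale SD 0.15.

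**Step 1: invariance.** For any constant a and any k > 0, corr(X, a + kY) = k·Cov(X, Y) / [SD(X)·k·SD(Y)] = corr(X, Y). This is exact and needs no assumption about the data.

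**Step 2: what each paired statistic shows.** Let d = log(one-stage) − log(chromogenic). The ratio is exp(mean d), and the limits of agreement are exp(mean d ± 1.96·SD of d).

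| True ratio k | Pearson r | Concordance coefficient | Paired geometric mean ratio | 95% limits of agreement |
|---|---|---|---|---|
| 1.00 | 0.984 | 0.98 | 0.98 | 0.77 to 1.25 |
| 1.53 | 0.984 | 0.84 | 1.51 | 1.18 to 1.92 |
| 1.74 | 0.984 | 0.77 | 1.71 | 1.34 to 2.18 |
| 2.00 | 0.984 | 0.68 | 1.97 | 1.54 to 2.51 |

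The value 0.984 reflects the assumed spread and error. That it stays the same in every row does not.

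**Step 3: what the planned separate summaries would show.** In the same data the chromogenic geometric mean is 28.9%, against 28.5, 43.6, 49.5 and 56.9% by one-stage for the four ratios. The share at or above 40% is 36% by chromogenic, against 30, 56, 64 and 70% by one-stage. These summaries move with the ratio, and the scatter plot would tilt away from the identity line.

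**Step 4: what the separate summaries leave out.**
- They describe each assay alone, so they give no confidence interval for a paired ratio and no numerical estimate of how it varies with level.
- Under SAP 3.2.4 and 3.2.5 both assays are set to 0.9% after prophylaxis is resumed, and after discontinuation for lack of efficacy. Such records show equality by construction. The scatter plots exclude data after resumption and impute nothing.
- They cover the central laboratory. Local one-stage results appear in the scatter plots and in r. Local FVIII values also enter the recovery calculation and listing in SAP 6.6.2, which is not an assay comparison.

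**Step 5: repeated samples.** The Year 1 schedule in Protocol 1.3 gives at least 12 × 2 = 24 FVIII samples to Week 12, 8 weekly samples in Weeks 13 to 20, 7 at two-week intervals in Weeks 22 to 34, and 4 in Weeks 38 to 52: 24 + 8 + 7 + 4 = 43 per participant before exclusions. SAP 6.2.5 does not say how repeated samples enter r.

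**The case against.** The strongest reply is that the comparison does not rest on r alone. The scatter plot is in the same bullet, and the by-visit levels, geometric means, categories and box plots by central assay would all reveal a sizeable proportional difference. That stands, as Step 3 shows. A reader might infer that the report would look the same whether the central assays agreed or differed nearly two-fold; the documents do not support that.

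A second reply is that the objective is an undefined exploratory comparison, and no text sets agreement or a conversion factor as its aim. That also stands, so it would be too strong to say that the plan cannot answer its stated objective.

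A third concerns Protocol 8.1.2.3. A reader might take 1.53 and 1.74 as the sponsor's conversion factors, or infer that the one-stage thresholds depend on such a conversion. The limits come from a separate management guide, refer to the local one-stage assay, and are not said to be derived from an assay ratio.

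Two smaller points also hold. It cannot be asserted that repeated samples will be pooled as independent, because the SAP is silent, and it attaches no interval or test to r. Nor does this correlation drive clinical decisions: Protocol 1.3 and 8.3.10 use individual local or central results as they arise.

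None of this supplies the missing paired estimate, or a summary of local one-stage levels.

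**Conclusion.** The point holds in a limited form. Pearson's r is the only paired numerical statistic planned for chromogenic against one-stage, and for central against local one-stage, and it is unchanged by a proportional or constant difference. The planned plots and central summaries would show a group-level difference between the central assays, but no paired size, confidence interval or change with FVIII level is planned. Local one-stage levels have no summary beyond the scatter plots and r.

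The invariance is exact. The values in the table, including r = 0.984, rest on the assumed distribution and error, so it cannot be said that the trial's own r will be close to 1.

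The effect is confined to an exploratory endpoint. The key secondary FVIII endpoint uses the central chromogenic assay, and Total and Treated ABR do not use FVIII activity, so no confirmatory result changes. This is a cheap improvement to make before database lock, not a threat to the trial's conclusions.

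**What to change.** Keep the scatter plots and r in SAP 6.2.5, and add:
- The paired geometric mean ratio (one-stage/chromogenic) with 95% CI, from a mixed model on the log ratio with participant as a random effect, using the same unimputed samples as the scatter plots.
- The same ratio by FVIII band, for which the SAP's reporting categories could serve, with sparse ones merged. Band on the mean of the two log values. If bands are set on chromogenic alone, label the result descriptive, because error in that assay enters both the band and the denominator of the ratio.
- A log-scale Bland-Altman plot with limits of agreement that allow for repeated samples per participant.
- The same outputs for chromogenic against local one-stage and for central against local one-stage, with a laboratory or site term, because Protocol 8.1.2.1 lets local laboratories follow their own practice.
- One sentence saying how repeated samples enter r.

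The threshold ratios 1.53 and 1.74 should not be presented as conversion factors, and no clinical threshold needs to change. The cost is a few lines of SAP text and an added exploratory model and plot for each pair, on data already paired for the scatter plots.

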6.2.6. Annualized FVIII Consumption

This endpoint will be analyzed similarly as AIR, including main analysis, timing of the analysis, and table presentation.

One sensitivity analysis will be performed to include only the data collected in the lead-in study (C0371004) and the data postinfusion of PF-07055480 using the same analysis model as described above. This analysis will be conducted on the 'Efficacy' population.

In addition, the annualized FVIII consumption from Week 12 through data cutoff will be analyzed using the 'Dosed' population (regardless of the length of follow-up preinfusion or postinfusion).

As supplementary analyses, annualized FVIII consumption in yearly intervals, as well as in cumulative follow-up intervals (i.e., from Week 12 through 2 years postinfusion, from Week 12 through 3 years postinfusion, etc.) as defined in [Section 3.1.1](#), will be tested separately using the same method as for the main analysis using the 'Efficacy' population to compare with the annualized FVIII consumption of FVIII prophylaxis replacement regimen as secondary endpoints.

6.2.7. Treated Annualized Bleeding Rate of Specific Type

This Treated ABR of specific type includes Treated ABR by:

- Cause (spontaneous or traumatic).
- Location type (in all joints, in target joints, or in soft tissue/muscle/other).

These endpoints will be analyzed using the same main analysis method as for Total ABR from Week 12 through at least 15 months (up to data cutoff) postinfusion and by yearly interval, as well as by cumulative follow-up interval post PF-07055480 infusion on the 'Efficacy' population. NI, superiority testing or sensitivity analyses will not be conducted for this endpoint. In addition, as a supplementary analysis, Treated ABR by cause within each location [i.e., (spontaneous, traumatic) x (joint, target joint, soft tissue/muscle/other)] from Week 12 through at least 15 months (up to data cutoff) post PF-07055480 infusion will

be summarized with descriptive statistics (without comparison to lead-in data) on the ‘Efficacy’ population.

6.2.8. Total ABR (treated and untreated bleedings) by Cause and by Location

Total ABR by cause and by location will be analyzed separately using the same main analysis method as for Total ABR from Week 12 through at least 15 months (up to data cutoff) postinfusion and by yearly interval as well as by cumulative follow-up interval post PF-07055480 infusion on the ‘Efficacy’ population. NI, superiority testing or sensitivity analyses will not be conducted for this endpoint. In addition, as a supplementary analysis, Total ABR by cause within each location [i.e., (spontaneous, traumatic) x (joint, target joint, soft tissue/muscle/other)] from Week 12 through at least 15 months (up to data cutoff) post PF-07055480 infusion will be summarized with descriptive statistics (without comparison to lead-in data) on the ‘Efficacy’ population.

6.2.9. Percentage of Participants without Bleeds

Percentage of participants without treated bleeds will be reported for the same time periods as for Total ABR: from Week 12 through at least 15 months (up to data cutoff) post PF-07055480 infusion, by yearly interval as well as by cumulative follow-up interval. The yearly intervals and cumulative follow-up intervals are defined in [Section 3.1.1](#).

The percentage of participants without treated and untreated bleeds will be reported for the same time periods as for Total ABR: from Week 12 through at least 15 months (up to data cutoff) post PF-07055480 infusion, by yearly interval as well as by cumulative follow-up interval.

The summary tables will be provided for the time periods mentioned above and will include the number of participants included in the specified time interval, frequencies, and the percentage of participants with or without bleeding. The ‘Efficacy’ population will be used for the summary.

In addition, the percentage of participants without treated and untreated bleeds from Week 12 through data cutoff post PF-07055480 infusion will be reported for the ‘Dosed’ population.

